8.5.2 Laboratory Assessments

The laboratory assessments require that blood samples for hematology and blood chemistry, and a urine sample for urinalysis are taken (Table 8-3, and Table 8-4). Laboratory assessments will be performed at the investigational site.

At Screening: all patients will have screening laboratory assessments including hematology and blood chemistry within 3 weeks (preferably 2 weeks in the Lutathera arm) before the projected first treatment date.

During the Treatment Phase (including cross-over and re-treatment):

- In the Lutathera arm: within 2 weeks before and 4±1 weeks after each Lutathera treatment. In addition, for the second, third, and fourth Lutathera treatment, an additional laboratory assessment will be performed on the same day, or within one day prior Lutathera administration. Blood tests performed 4 weeks after any treatment cannot serve as baseline values for the next treatment. After the end of Lutathera treatment, laboratory assessments will be performed every 12±1 weeks (see Table 8-2 and Visit Schedule in Table 8-3).
- In the 60 mg octreotide long-acting arm: throughout the study laboratory assessments will be performed 4 weeks (+3 days) after the first treatment till Week 28, and every 12+1 weeks from Week 36 onwards (see Visit Schedule in Table 8-4).

In the event of a significant laboratory abnormality, or if clinical or laboratory evidence of toxicity occurs, the Investigator will collect additional specimens for repeat or additional analyses, at intervals appropriate to the abnormality. The patient will be closely followed until sufficient information is obtained to determine the cause or the value regresses. Appropriate remedial measures should be taken and the response recorded.

All safety laboratory results must be evaluated by the Investigator before administration of study medication.

Any clinically relevant change from baseline onwards will be recorded on the Adverse Event page of the e-CRF, possibly with a single diagnosis encompassing all changes possibly supporting to the single diagnosis.

During the COVID-19 pandemic, the investigator should consider whether it is possible to arrange for the laboratory tests to be performed at a local laboratory for those patients who cannot come to the clinical site as scheduled. The investigator should collect and file all local lab reports in the patient medical record or chart.

Haematology	Blood Chemistry	Pregnancy test
 WBC with differential² Platelets² Hb² MCV Haematocrit 	 Blood Chemistry BUN or urea Serum creatinine³ Creatinine Clearance³ Uric acid Albumin 	 Pregnancy test Pregnancy test, if applicable (urine pregnancy test is accepted⁵)
	 Total bilirubin³ AP AST/ASAT ALT/ALAT Gamma-GT Sodium Potassium 	
	 Magnesium LDH CgA⁴ GlycoHb (haemoglobin A1C) 	

Table 8-2. Laboratory Assessments¹.

• TSH (and free Thyroxine (fT4) if TSH is abnormal)
Calcium
Fasting blood Glucose

¹ Laboratory assessments performed on the same day or within one day prior to administration of the second, third, and fourth doses of Lutathera must include at minimum:

- serum urea or blood urea nitrogen and creatinine (including creatinine clearance calculation)
- serum potassium, serum total bilirubin, aspartate aminotransferase and alanine aminotransferase
- hemoglobin, platelet count, total leukocyte count, and absolute neutrophil count.
- ² Before each Lutathera dose, patients must meet the criteria for Hb, WBC, and platelets, as defined in the inclusion criteria, at baseline and before each subsequent treatment. If the patient cannot be retreated due to haematological abnormalities, the evaluation must be repeated at least once weekly until re-treatment.
- ³ Before each Lutathera dose, patients must meet the criteria for creatinine clearance and total bilirubin as defined in the eligibility criteria at baseline and before every re-treatment. As entry criterion, patients must not have creatinine clearance <40 mL/min calculated by the Cockroft Gault method. During the course of the study, if in the Lutathera arm a 40% increase over the baseline serum creatinine value occurs during the course of treatment, or a decrease of over 40% in creatinine clearance as calculated from serum creatinine concentrations according to Cockcroft-Gault formula, DMT rules must apply (Table 6-4) and patients must also have a measured creatinine clearance (or GFR) performed. Measured creatinine clearance should be through a 24-h urine collection. Total urinary protein should also be measured in this collection. If the measured urinary creatinine clearance shows decrease of \leq 40% compared to baseline, treatment can continue.

The Cockcroft-Gault formula allows this estimation based on the occurrence of creatininemia, and correlating patient muscular mass (and so the consequent creatinine production) to weight, gender and age:

```
Est. Creatinine Clearance = [[140 - age (yr)]^*weight (kg)]/[72^*serum Cr(mg/dL)] (multiply by 0.85 for women)
Or
```

*Est. Creatinine Clearance = [[140-age(yr)]*weight (kg)]/[0.814* serum Cr(umol/L)]* (multiply by 0.85 for women)

⁴ In South Korea only, CgA assessment being discontinued in Q3 2022 due to lab kits shortage

⁵ For UK, serum pregnancy test is mandatory at baseline

During the Follow-up Phase, in both study arms laboratory assessments (hematology and blood chemistry) will be performed every 6 months (± 1 month).

8.5.3 **Pregnancy Test**

Women who receive Lutathera in the study, including those who crossed over to Lutathera and those re-treated with Lutathera, should not procreate during Lutathera treatment and until six months after the end of their last treatment with Lutathera, or until the end of treatment period of the study, whichever is longer. Women in the control arm should not procreate until the end of treatment period.

A pregnancy test (either on urine or blood) must be performed at baseline and within 14 days (preferably 7 days) prior to each Lutathera treatment for every female patient of childbearing potential (Section 5 and Appendix 1).

Ionizing radiations of lutetium (177Lu) oxodotreotide may potentially have temporary toxic effects on female and male gonads (decrease of inhibin-B and concomitant increase of FSH, suggesting radiation damage to Sertoli cells). Fertility is usually restored 12 to 18 months after treatment. The participant will be recommended to seek genetic consultation before starting treatment if the patient wishes to have children after treatment, which includes the option of cryopreservation of sperm or eggs before treatment starts.

For UK only:

A pregnancy test (blood) must be performed at baseline in both arms and within 7 days prior to the first Lutathera treatment. A urine or blood pregnancy test must be performed within 7 days prior to each Lutathera treatment for every female patient of childbearing potential (Section 5 and Appendix 1). A urine or blood pregnancy test must be performed in both arms at the end of the relevant systemic exposure to octreotide.

For Germany only:

A pregnancy test must be performed at baseline in both arms (either on urine or blood). In the Lutathera arm, a urine or blood pregnancy test must be performed monthly during the treatment phase (within 7 days prior to each Lutathera treatment) (Section 5 and Appendix 1) and for the following six months after the end of treatment with Lutathera for every female patient of childbearing potential.

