	Recurrent Grade 3 or 4	If AE resolves within 9 – 16 weeks after the previous dose, resume Lutathera at 3.7 GBq (100 mCi). If reduced dose does not result in Grade 3 or 4 anemia, administer Lutathera at 7.4 GBq (200 mCi) for next dose. If AE does not resolve within 16 weeks after the previous dose, permanently discontinue Lutathera. Permanently discontinue Lutathera.
Neutropenia	First occurrence of:	Withhold dose until complete or
	Grade 3 (ANC < 1.0 - 0.5 x 10 ⁹ /L) Grade 4 (ANC < 0.5 x 10 ⁹ /L)	If AE resolves before next planned Lutathera dose (i.e. within 9 weeks after the previous dose), administer next full dose of Lutathera (7.4 GBq / 200 mCi). If AE resolves within 9 – 16 weeks after the previous dose, resume Lutathera at 3.7 GBq (100 mCi). If reduced dose does not result in Grade 3 or 4 neutropenia, administer Lutathera at 7.4 GBq (200 mCi) for next dose. If AE does not resolve within 16 weeks after the previous dose, permanently discontinue Lutathera.
	Recurrent Grade 3 or 4	Permanently discontinue Lutathera.
Renal Toxicity	 First occurrence of: Creatinine clearance less than 40 mL/min; calculated using Cockcroft Gault formula with actual body weight, or 40% increase from baseline serum creatinine, or 40% decrease from baseline creatinine clearance; calculated using Cockcroft Gault formula with actual body weight. 	Withhold dose until complete resolution. If AE resolves before next planned Lutathera dose (i.e. within 9 weeks after the previous dose), administer next full dose of Lutathera (7.4 GBq / 200 mCi). If AE resolves within 9 – 16 weeks after the previous dose, resume Lutathera at 3.7 GBq (100 mCi). If reduced dose does not result in renal toxicity, administer Lutathera at 7.4 GBq (200 mCi) as next dose.

		If AE does not resolve within 16 weeks after the previous dose, permanently discontinue Lutathera.
	Recurrent renal toxicity Grade 3 or 4	Permanently discontinue Lutathera.
Hepatotoxicity	First occurrence of: Bilirubinemia greater than 3 times the upper limit of normal (Grade 3 or 4), or	Withhold dose until complete or partial resolution (Grade 0, 1 or 2). If AE resolves before next planned Lutathera dose (i.e. within 9 weeks after the previous dose), administer next full dose of Lutathera (7.4 GBq / 200 mCi).
		If AE resolves within 9 – 16 weeks after the previous dose, resume Lutathera at 3.7 GBq (100 mCi). If reduced Lutathera dose does not result in G3 or 4 bilirubinemia, administer Lutathera at 7.4 GBq (200 mCi) as next dose.

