		If AE does not resolve within 16 weeks after the previous dose, permanently discontinue Lutathera.
	Defined as: Hypoalbuminemia less than 30 g/L with International Normalized Ratio (INR) >1.5.	 Withhold dose until complete or partial resolution (Grade 0 to 1). If AE resolves before next planned Lutathera dose (i.e. within 9 weeks after the previous dose), administer next full dose of Lutathera (7.4 GBq / 200 mCi). If AE resolves within 9 – 16 weeks after the previous dose, resume Lutathera at 3.7 GBq (100 mCi). If reduced Lutathera dose does not result in G2, 3 or 4 hypoalbuminemia, administer Lutathera at 7.4 GBq (200 mCi) as next dose. If AE does not resolve within 16 weeks after the previous dose, permanently discontinue Lutathera.
	Recurrent hepatotoxicity	Permanently discontinue Lutathera.
Any other CTCAE* Grade 3 or Grade 4 AE ¹	rirst occurrence of Grade 3 or 4	partial resolution (Grade 0 to 2).

		If AE resolves before next planned Lutathera dose (i.e. within 9 weeks after the previous dose), administer next full dose of Lutathera (7.4 GBq / 200 mCi).
		If AE resolves within 9 – 16 weeks after the previous dose, resume Lutathera at 3.7 GBq (100 mCi). If reduced dose does not result in Grade 3 or 4 toxicity, administer Lutathera at 7.4 GBq (200 mCi) as next dose.
		If AE does not resolve within 16 weeks after the previous dose, permanently discontinue Lutathera.
	Recurrent Grade 3 or 4	Permanently discontinue Lutathera.
Severe heart failure	NYHA class III or IV	Permanently discontinue Lutathera.
¹ No dose modification requir *CTCAE: Common Termino	red for hematological toxicities Grade 3 logy Criteria for Adverse Events, Natior	or Grade 4 solely due to lymphopenia nal Cancer Institute

In addition,

- permanently discontinue treatment with Lutathera if hypersensitivity due to the active substance or any of excipients of Lutathera is observed;
- Temporarily discontinue treatment with Lutathera, until resolution or stabilisation before treatment can be resumed.
 - Occurrence of an intercurrent disease (e.g. urinary tract infection);
 - Major surgery: wait 12 weeks after the date of surgery, then restart the treatment with Lutathera.

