After resolution of a DMT, a patient may receive subsequent planned treatment(s) at the full dose (if resolved within 9 weeks after the previous dose), or at 50% of the standard treatment dose (if resolved within 9 - 16 weeks after the previous dose), if this is felt to be safe for the patient, or the risk-benefit assessment is favourable. If the same DMT reoccurs after treatment with the reduced Lutathera dose, the patient will remain in the study and continue the scheduled clinical / tumor assessments until tumor progression, but no further Lutathera treatment will be given. Octreotide long-acting 30 mg will be continued at monthly intervals. If the DMT event does not reoccur, the next treatment is at full dose, if it is considered to be safe for the patient, or the risk-benefit assessment is favourable.

If a patient experiences a DMT during Lutathera therapy, subsequent treatments with Lutathera are permissible, provided the DMT resolves within 16 weeks following the non-tolerated administration. In any case, the patient will continue the administration of 30 mg octreotide long-acting.

Lutathera overdose, has a very low probability of occurring since it will be supplied as a single dose "ready to use product" in order to avoid any manipulation outside the production facilities. In addition, the infusion system methods do not allow the concurrent use of two separate Lutathera solution vials (see pharmacy manual). No doubling of the administered radioactivity is ever allowed either in absolute amount or by shortening the time intervals between treatments. Treatments (amount of radioactivity and time of administration) will be monitored during the study and any unallowed treatment modification will be considered a major protocol violation.

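### Table 6-4 and Table 8-2 footnote 3 give conflicting Lutathera instructions for the same kidney result; the white-cell and renal-recurrence rules have narrower inconsistencies

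*Protocol*

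**What the plan says.** **Kidney.** The renal row of Table 6-4 (Protocol Section 6.5.2.1) has three first-occurrence triggers: calculated clearance below 40 mL/min, "40% increase from baseline serum creatinine", or "40% decrease from baseline creatinine clearance". The action is "Withhold dose until complete resolution". The next dose is full if the event resolves within 9 weeks of the previous dose and half if it resolves at 9 to 16 weeks. Lutathera stops permanently if the event has not resolved by 16 weeks. The row does not mention a measured clearance.

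Table 8-2 footnote 3 (Section 8.5.2) opens by requiring the entry clearance limit (not below 40 mL/min) before each dose. It then repeats the two 40% triggers, makes the Table 6-4 rules mandatory and adds a measured clearance from a 24-hour urine collection. Its last sentence starts "If the measured urinary creatinine clearance shows decrease of" and, for a fall of 40% or less, permits treatment to continue.

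**White cells.** Table 6-4 footnote 1 waives dose modification for haematological toxicity of Grade 3 "or Grade 4 solely due to lymphopenia". Table 8-2 footnote 2 says: "Before each Lutathera dose, patients must meet the criteria for Hb, WBC, and platelets", with weekly repeats until they do. The WBC limit is in exclusion criterion 2 (Section 5.2): below 2 x 10^9/L excludes. Section 10.1.5 lists Grade 3 or 4 leukopenia as dose-modifying. Neither footnote 2 nor Section 10.1.5 has a lymphopenia exception.

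**Renal recurrence.** The Table 6-4 stopping row reads "Recurrent renal toxicity Grade 3 or 4". The text after the table says "If the same DMT reoccurs after treatment with the reduced Lutathera dose, the patient will remain in the study", without further Lutathera, and states no grade. A later, general sentence there allows further doses if a DMT resolves within 16 weeks of the dose that was not tolerated.

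**The concern.** A site with a patient whose creatinine is up 50% can hold the dose under Table 6-4 or continue under footnote 3, and either choice has protocol text behind it. Section 6.5.2.1 treats any unallowed treatment modification as a major protocol violation, so following one page may breach the other.

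The kidney and bone marrow are the organs that Section 10.1.5 singles out as critical. Section 4.5 names the dose-modifying rules among the subject safeguards, and Section 10.2 provides no additional data monitoring. Lutathera delays, modifications and relative dose intensity are reported outputs (SAP Sections 2.4.1.3 and 2.4.1.4), so they would partly reflect which page a site followed.

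Randomization was complete at 222 patients when Protocol version 2.0 was issued. Cross-over and re-treatment may start up to four years after the last randomization, and Section 8.5.2 applies its laboratory rules to both.

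**Working it through.** The plan states no figure to reproduce. The check sets the passages side by side and converts the two 40% limits to one scale.

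**1. Kidney: common scale.** Inputs are the 40% limits in Table 6-4 and footnote 3, and the Cockcroft-Gault formula in Section 8.5.2. At fixed age and weight, clearance is proportional to 1/creatinine.

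- Creatinine up 40%: 1 - 1/1.40 = 0.286, a 28.6% fall in calculated clearance.
- Clearance down 40%: 1/(1 - 0.40) = 1.667, a 66.7% rise in creatinine.

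The creatinine trigger is therefore met well before clearance has fallen 40%. If the 24-hour measurement agrees with the estimate, a rise of 40% to 66.7% meets the Table 6-4 hold and also passes the release in footnote 3. No discordant test is needed. Above that range, release requires a measured fall smaller than the calculated one.

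**2. Kidney: effect of the 40 mL/min floor.** Footnote 3 also blocks dosing below 40 mL/min, which limits the conflict:

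- at a 40% rise, baseline/1.40 must be at least 40, so baseline must be at least 56 mL/min;
- at a 66.7% rise, baseline x 0.60 must be at least 40, so baseline must be at least 66.7 mL/min.

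Below a baseline of 56, a 40% rise takes calculated clearance under 40 and both passages hold the dose.

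**3. Kidney: illustration (assumed patient).** Man, 60 years, 75 kg, creatinine 80 umol/L: (140 - 60) x 75 / (0.814 x 80) = 92.1 mL/min. At creatinine 112 (up 40%), clearance is 65.8, down 28.6%. At 133 (up 66.7%) it is 55.3, down 40%. Throughout, Table 6-4 withholds; if measured clearance matches, footnote 3 lets treatment continue.

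**4. White cells.** Appendix 7 grades WBC below 2.0 to 1.0 x 10^9/L as Grade 3. Assumed counts: neutrophils 1.5 + lymphocytes 0.3 + other 0.1 = 1.9. The neutropenia trigger (below 1.0) is not met. Table 8-2 footnote 2 blocks the dose; Table 6-4 footnote 1 waives modification if the low count is attributed solely to lymphopenia. For WBC below 2 from another cause the texts agree, because the Table 6-4 row for other Grade 3 or 4 events holds until Grade 0 to 2.

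**5. Renal recurrence.**

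| Situation | What the text provides |
|---|---|
| Recurrence at Grade 3 or 4 | Table 6-4: stop permanently |
| Recurrence after a reduced dose, below Grade 3 | Outside the stopping row; text after the table: no more Lutathera, no grade stated |
| Recurrence after a full dose, below Grade 3 | No renal-specific line; only the general 16-week sentence |

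The first-occurrence triggers are ungraded and the stopping row is graded. The recurrent-hepatotoxicity row has no grade limit.

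**The case against.** **Kidney.** Footnote 3 can be read as a confirmatory step inside the dose-modifying rules: it invokes Table 6-4, adds a better measurement, and its release is permissive. It does not say that the next dose precedes resolution, or at what activity. A reader might infer that every patient with a 40% to 66.7% rise gets opposite orders. The documents do not support that, since it requires measured clearance to follow the estimate and remain above the floor. What stands is that Table 6-4 neither contains nor cites this step, and nothing says whether the complete-resolution hold and the 9- and 16-week steps lapse once the measurement is in.

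**White cells.** The SAP laboratory grading treats neutrophils of 2 x 10^9/L or more as Grade 0, so any WBC below 2 implies at least a mildly low neutrophil count on that scale. Attribution solely to lymphopenia is then contestable, and the result could be classed as leukopenia and held. This narrows the conflict without removing it: footnote 1 relies on attribution, while footnote 2 and Section 10.1.5 do not.

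**Recurrence.** A reader might infer that Table 6-4 and the later text contradict each other after a reduced dose. In substance they do not: the first-occurrence row returns to full dose only if the reduced dose causes no renal toxicity, with no grade limit. The defect is the mismatch with the graded stopping row, and mainly the gap after a full dose.

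**Safeguards.** Investigators must review laboratory results before dosing and consult specialists as needed (Sections 8.5.2 and 6.5.2). That limits harm but does not tell them which instruction governs.

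**Conclusion.** The kidney inconsistency is established. For creatinine rises of 40% to 66.7%, one passage holds Lutathera and the other lets it continue. This assumes fixed age and weight, measured clearance that tracks the estimate, and clearance of at least 40 mL/min (baseline at least 56 mL/min at the lower end of the range and 66.7 at the upper). The documents do not show how many patients fall there.

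The white-cell conflict is confined to WBC below 2 x 10^9/L attributed solely to lymphopenia. A reader might size it from the Grade 3 or 4 lymphopenia rate quoted for the earlier phase III trial in Section 4.5; that is a different event, and the documents give no rate for this one.

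The recurrence defect is an ungraded trigger paired with a Grade 3 or 4 stopping row. A reader might measure the gap with the SAP creatinine grades, but that is a programmed analysis scale, and the Appendix 7 extract given to sites has no creatinine or kidney term. The width of the gap is therefore not established.

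Nor does the primary PFS inference change: it is analysed as randomized and ignores treatment discontinuation (SAP Sections 2.5.2 and 2.5.3). The consequence is for patient safety and consistent dosing, mainly in the remaining cross-over and re-treatment cycles.

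**What to change.** The sponsor's clinical team should reconcile Table 6-4, the recurrence text after it, Section 10.1.5 and Table 8-2 footnotes 2 and 3 into one rule per parameter, printed once and cross-referenced elsewhere. The text should state:

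- whether, and how, a measured clearance affects the renal hold, the complete-resolution requirement and the 9- and 16-week dose steps;
- whether the pre-dose WBC criterion applies when the low count is due solely to lymphopenia;
- one renal recurrence criterion, in terms consistent with the first-occurrence triggers, covering recurrence after both full and reduced doses.

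This review does not say which rule is right. The cost is a wording change in the next amendment, the route Section 14.1 requires, with a letter to alert sites. No new procedure or data collection is needed.
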